5.5.3 Dose delays

In the event of toxicity, treatment should be delayed for up to two weeks until these toxicities have resolved to Grade ≤ 1 or returned to baseline. If there is no recovery after a two week delay, the patient should be withdrawn from the trial.

Intermittent dosing schedules may be explored based on observed toxicities, PK and PD data.

5.6 Missed Doses

Patients should take the correct number of AZD3965 capsules at the same time(s) every day.

Should a patient miss a scheduled dose in error, for example, forgetting to take the drug, then AZD3965 may be administered up until 12 hours after the scheduled dosing time (this applies to once a day dosing only). If it is not taken within this time then the patient should wait until the next scheduled dose and continue as per normal drug administration.

If the dosing schedule is twice daily dosing and the patient should miss a dose in error, then AZD3965 may be administered up until two hours after the scheduled time of dose. If it is not taken within this time then the patient should wait until the next scheduled dose and continue as per normal drug administration. Any missed doses should be recorded in the patient diary card.

An occasional shift in dosing may be permitted by CDD, to accommodate study visits and study assessments. This must be discussed and agreed in advance. On these occasions dosing should be brought back to the original dosing schedule as soon as possible.

Should a patient vomit after taking the drug, then the patient should be instructed not to take another capsule until their next scheduled dosing time.

5.7 Duration of treatment

Treatment should continue for six cycles unless (a) the patient asks to be withdrawn, (b) there is evidence of disease progression (c) the patient is experiencing unacceptable toxicity or (d) the Investigator feels the patient should be withdrawn from any other reason including those listed in Section 12.

If a patient is benefiting from treatment with AZD3965 (i.e. has stable or responding disease as measured by RECIST version 1.1 or International Working Group criteria for Lymphoma) and the patient is not experiencing any Grade 2 or greater drug-related AEs then the CI and / or Principal Investigator (PI) can ask the CDD if the patient can continue with treatment. The CDD will request a full toxicity profile of that patient when considering the request. Should the decision be to allow further treatment, 6 further cycles may be given. After completion of 12 cycles, a further review will be conducted by the Sponsor, CI and treating clinician(s). A patient may continue on study as long as they are benefiting from treatment with AZD3965 and IMP stock is available. If the CDD decides not to allow the patient to

continue treatment, based on the information provided or on other information received, then the CDD's decision is final.

For the purposes of this trial a patient who completes six or more treatment cycles is considered to have completed the trial.

For patients who continue on study for extended treatment, i.e. for longer than 6 or 12 cycles, these patients must continue to show that benefit is being derived from receiving AZD3965. After each disease assessment the PI will relay findings to CDD for this determination to be met.

5.7.1 Replacement of patients

In **Part 1**, patients were replaced if they fulfilled the following criteria and three evaluable patients had not yet been treated at the same dose level:

• Patients who miss more than 25% of their first AZD3965 cycle (for reasons other than drug related toxicity).

Patients who missed more than 50% of their first AZD3965 cycle due to toxicity which was not dose limiting were discussed between the CDD and CI and a decision will be taken on whether the patient should be replaced by another at the same dose level.

Patients could be replaced if they were unable to complete

as to whether to replace such a patient depended on the status of the other patients within that cohort ERG data already obtained at that dose level. This

decision was made by the CDD in consultation with the CI.

In **Part 2**, patients will be replaced in this phase if they fulfil the following criteria:

• Patients who miss more than 25% of their first AZD3965 cycle (for reasons other than drug related toxicity).

Patients who complete more than 75% of their first AZD3965 cycle (for reasons other than drug related toxicity) but fulfil one of the following additional criteria may also be replaced in Part 2. This will be discussed on a per patient basis between the Investigator, CI and CDD.

5.8 Concomitant medication and treatment

Concomitant medication may be given as medically indicated. Details (including doses, frequency, route and start and stop dates) of the concomitant medication given must be recorded in the patient's medical records but only the medication name, start date and stop date is required to be entered into the electronic case report form (eCRF).

Radiotherapy may be given for the control of bone pain; however this cannot be given concomitantly during AZD3965 administration. Please note that in exceptional circumstances, if the patient's radiotherapy cannot be completed within a two week period, this may be extended to three weeks after consultation with CDD. Irradiated lesions will not be evaluable for response.

The patient must not receive other anti-cancer therapy or investigational drugs while on the trial.

Patients may continue the use of bisphosphonates for bone disease and corticosteroids provided the dose has not been changed in the two weeks prior to administration of the first dose of AZD3965 and is not altered during the first 15 days post administration of AZD3965 on Day 1.

For patients who require prednisolone (or equivalent) for a short duration to improve their quality of life during screening, this is acceptable,

The concomitant administration of potent CYP3A inhibitors, specifically: protease inhibitors (atanazavir, indinavir, nelfinavir, ritonavir, saquinavir), macrolide antibiotics (clarithromycin, telithromycin), azole antifungals (ketoconazole, itraconazole, voriconazole), nefazodone should be avoided.

The concomitant administration of CYP3A inducers, specifically: rifampicin, rifapentine, rifabutin, phenytoin, carbamazepine, phenobarbitol, St John's Wort should also be avoided.

An up to date list of CYP3A inhibitors and inducers can be found at https://drug-interactions.medicine.iu.edu/Clinical-Table.aspx.

Drugs with a known risk of inducing TdP should not be taken during the trial. These drugs (see Appendix 3) have been sourced from https://www.crediblemeds.org. As drugs are reviewed on an ongoing basis to assure that the available evidence supports their continued placement on this list, the list changes regularly. **Therefore, check the website at crediblemeds.org for the most up-to-date information.** If these drugs are to be used in an emergency once the patient is off AZD3965 treatment, they should be taken a minimum of 24 hours after the patient's last dose of AZD3965. Before a patient re-starts AZD3965 treatment, a maximum of 5 half-lives of the concomitant drug must be reached.

If a patient is taking any dietary supplements or complementary medicines/botanicals, the CDD must be informed at the earliest opportunity.

Use of potential prohibited concomitant medications will be discussed on a patient by patient basis with the CDD and CI before a patient is enrolled on the study.

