2.2.7.2 Predictive pharmacology based approach

2.2.8 Starting dose

2.2.9 Maximum Exposure

Based on the nature of adverse effects observed in non-clinical studies, dose escalation to maximum tolerated dose would not be appropriate for AZD3965 in man. Dose escalation could be stopped based on pharmacodynamic (PD) effects, e.g. PBMC lactate accumulation. However, there is limited clinical experience with the planned PD assays in this study, and these assays alone are not felt to be sufficient to inform dose escalation decisions with the appropriate degree of certainty. Instead an upper limit to the dose escalation of AZD3965 has been based on exposure levels.

In the CRUKD/12/004 trial, patients will undergo extensive clinical monitoring for potential retinal toxicity, which is expected to be reversible should it occur. A maximum AZD3965 exposure limit in humans is therefore set as a dose of AZD3965 producing a C_{max} not in excess of 5 µM and an AUC not in excess of 20 µmol•h/L. These levels of AZD3965 should allow dose escalation into the anticipated therapeutic range while remaining below the levels likely to affect retinal function. These levels may produce some QTc effects but these are likely to be minor and short-lived post-dosing. Based on extrapolation from nonclinical data, these exposure levels might be reached with a daily dose of around 500 mg/day.

Assessments of exposure will be based on Day -7, Day 1 and Day 29 pharmacokinetics from Part 1. If pharmacokinetics from any of these analyses indicate that the exposure cap has been exceeded the cohort will be completed (toxicity permitting) but no further dose escalations will take place. Pharmacokinetic data from all patients in a cohort must be available prior to dose escalation. If the drug demonstrates a good safety profile at doses producing exposures close to the planned cap a substantial amendment will be requested to allow further dose escalation.

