3.2 Patient evaluability

Part 1:

All patients that met the eligibility criteria and take at least one dose of AZD3965 were evaluable for safety decisions.

[figure not shown]
Patients who received less than 75% of their first continuous treatment cycle (for reasons other than toxicity) would not be evaluable for dose escalation decisions. Patients who completed 75% of their first continuous treatment cycle but did not complete the end of Cycle 1 ERG and ophthalmology assessments could also not be evaluable for dose escalation decisions. This was discussed on a per patient basis between the Investigator, Chief Investigator (CI) and CDD.

Part 2:

All patients that meet the eligibility criteria and take at least one dose of AZD3965 will be evaluable for safety decisions.

All patients who meet the eligibility criteria and take at least 75% of their first continuous treatment cycle (28 days) of AZD3965 and have a baseline assessment of disease will be evaluable for response.

To be assigned a status of complete response (CR) or partial response (PR), changes in tumour measurements must be confirmed by repeat measurements performed no less than four weeks after the response criteria are met. To be assigned a status of stable disease (SD), follow-up measurements must have met the SD criteria at least once and at least six weeks after the initial dose of the IMP AZD3965 is given.

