5. LVEF>50%

6. 18 years or over7. Written (signed and dated) informed consent and be capable of co-operating with treatment and follow-up

4.1.2 Exclusion criteria:

- Radiotherapy (except for palliative reasons), endocrine therapy, immunotherapy or chemotherapy during the previous four weeks (six weeks for nitrosoureas, Mitomycin-C and 4 weeks for investigational medicinal products) before treatment.⁵ Shorter wash out periods may be acceptable if patient has recovered from therapy related toxicity and is at least five terminal half-lives post last administration. This should be discussed and agreed with the CDD and CI.
- 2. Ongoing toxic manifestations of previous treatments greater than NCI CTCAE Grade 1 at the time of starting study treatment. Exceptions to this are alopecia or certain Grade 2 toxicities, which in the opinion of the Investigator and the CDD should not exclude the patient.
- 3. Symptomatic brain or leptomeningeal metastases.
- 4. Patients with known retinal disease or macular degeneration affecting visual acuity as assessed by ophthalmologic tests.
- 5. Female patients who are able to become pregnant (or are already pregnant or lactating). However, those patients who have a negative serum or urine pregnancy test before enrolment and agree to use two forms of contraception (one highly effective form plus a barrier method) [oral, injected or implanted hormonal contraception and condom; intra-uterine device and condom; diaphragm with spermicidal gel and condom] or agree to sexual abstinence, effective from the first administration of AZD3965, throughout the trial and for six months afterwards are considered eligible.⁶
- 6. Male patients with partners of child-bearing potential (unless they agree to take measures not to father children by using a barrier method of contraception [condom plus spermicide] or to sexual abstinence effective from the first administration of AZD3965, throughout the trial and for six months afterwards. Men with partners of child-bearing potential must also be willing to ensure that their partner uses an effective method of contraception for the same duration for example, hormonal contraception, intrauterine device, diaphragm with spermicidal gel or sexual abstinence). Men with pregnant or lactating partners must be advised to use barrier method contraception (for example, condom plus spermicidal gel) to prevent exposure of the foetus or neonate.⁶

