5.5 Dose modifications

5.5.1 Dose withdrawal

In the event of CTCAE Grade 3 or 4 QTc prolongation (QTc interval >500 msecs or increase of >60 msecs from baseline (QTcF correction)) treatment with AZD3965 will be withdrawn.

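### Section 5.8 sets the wash-out before AZD3965 restarts as a maximum of five half-lives, where a minimum is meant

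*Protocol*

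**What the plan says.** Section 5.8 deals with torsade-risk drugs in three steps.

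- A general bar: "Drugs with a known risk of inducing TdP should not be taken during the trial".
- If such a drug is needed in an emergency once the patient is off AZD3965, a gap from the last AZD3965 dose: "they should be taken a minimum of 24 hours after" that dose.
- For the return to treatment: "Before a patient re-starts AZD3965 treatment, a maximum of 5 half-lives of the concomitant drug must be reached".

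The section ends by saying that use of potentially prohibited medication "will be discussed on a patient by patient basis with the CDD and CI before a patient is enrolled on the study".

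Four other places bear on the point.

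- Section 4.1.2, exclusion criterion 1, accepts a shortened wash-out of earlier therapy if, among other conditions, the patient "is at least five terminal half-lives post last administration".
- Section 5.5.1 makes a QTc interval above 500 msec, or a rise of more than 60 msec, a reason to stop: "increase of >60 msecs from baseline (QTcF correction)) treatment with AZD3965 will be withdrawn".
- Section 2.2.9 says of the exposure cap: "These levels may produce some QTc effects but these are likely to be minor and short-lived post-dosing".
- Section 3.2 requires Part 2 patients to "take at least 75% of their first continuous treatment cycle (28 days) of AZD3965" to be evaluable for response.

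**The concern.** A wash-out before restarting a drug exists to guarantee a minimum clearance of the other drug. The restart sentence gives the number as a ceiling. The verb in the same sentence makes it a condition to be met first, so the two halves point in opposite directions.

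The drugs concerned are those the protocol otherwise excludes because they can cause torsade de pointes. A site that took the ceiling literally could resume AZD3965 while such a drug was still present. If QTcF then crossed the Section 5.5.1 limits, AZD3965 would be withdrawn, and that section states no exception for cause. The same limits are a dose-limiting toxicity criterion in Section 3.1.4 when the event is judged probably or highly probably drug related. Residual concomitant drug would make that judgement harder, since Section 10.2.4 lists concomitant medication among the alternative explanations to weigh.

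**Working it through.** **Direction of the bound.** The protocol gives no calculation for this rule, so the first check is of the text.

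| Place | What is timed | Direction |
|---|---|---|
| 5.8, emergency use | last AZD3965 dose to emergency drug | lower bound, 24 hours |
| 5.8, restart | clearance of emergency drug before AZD3965 resumes | worded as an upper bound, five half-lives, but to be met first |
| 4.1.2, exclusion 1 | clearance of earlier therapy before entry | lower bound, five half-lives |

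The restart sentence can be read in three ways.

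1. *Strict ceiling.* The wait may be anything from zero to five half-lives, and a restart after more than five would be barred. The bar has no evident purpose.
2. *No more than five half-lives need be waited.* This still sets no minimum and does not fit the verb.
3. *Floor of five half-lives.* This fits the verb and the purpose but requires the reader to reverse the key word.

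The version 13.0 entry in the amendment history describes the rule as allowing a restart only once five half-lives have passed. That supports reading 3 as the intent. It is context only and does not replace the current text.

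The closing sentence of Section 5.8 does not fill the gap, because its case-by-case discussion takes place before enrolment, not at a restart.

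**Residual drug at restart.** Assumption: first-order elimination, which the protocol does not state. The fraction remaining after *n* half-lives is 0.5^*n*.

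| Half-lives waited | Remaining |
|---|---|
| 0 | 100% |
| 1 | 50% |
| 2 | 25% |
| 3 | 12.5% |
| 4 | 6.25% |
| 5 | 3.125% |

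Under the literal ceiling every row is allowed. Under the floor only the last row, or less, is allowed. The ratio of the extremes is 100 / 3.125 = 32.

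**What the intended rule costs in Cycle 1.** Section 3.2 needs 75% of a 28-day cycle, so the allowance is 0.25 × 28 = 7 days. A wash-out of five half-lives uses all of it when the half-life is 7 / 5 = 1.4 days, or 33.6 hours. The half-lives below are assumed for illustration, and the 24-hour gap before the emergency drug is not counted.

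| Half-life | Wash-out (5 × half-life) | Share of 28 days |
|---|---|---|
| 6 h | 30 h = 1.25 days | 4.5% |
| 24 h | 120 h = 5 days | 17.9% |
| 72 h | 360 h = 15 days | 53.6% |

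Only the 72-hour example passes 25%.

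**The case against.** The strongest reply is that the sentence still works. A threshold that has to be met before an action is a precondition whatever adjective precedes it, and the strict-ceiling reading is absurd because it would forbid a longer wait. On this view it is a drafting slip with recoverable meaning. The amendment history confirms the direction.

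The comparisons are also looser than they look. The 24-hour rule covers the opposite sequence. Exclusion criterion 1 covers earlier cancer therapy and is a discretionary shortening of a four-week wash-out. Neither strictly contradicts the restart sentence.

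The chain to harm is conditional at each step: emergency use, a restart, a site choosing the wrong reading, residual drug, and then a QTcF limit crossed. ECGs with manual QTcF are weekly in Cycles 1 and 2 and two-weekly to Cycle 12 (Section 8.4), and a cardiologist reviews abnormal traces before dosing. The 32-fold figure is just 2^5.

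Much of this stands. The only true contradiction lies within the sentence itself; the other passages are analogies that show the intended direction. The situation is narrow, and the protocol expects AZD3965's own QTc effect at the exposure cap to be small, so the worry is the residual concomitant drug.

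It does not follow that the wording can stay. The visible text ties no ECG to a restart: the 24-hour ECG follows the first dose only (Section 8.3), and from Cycle 13 ECGs are done as necessary (Section 8.5). Recoverable intent is a weak safeguard for a dosing instruction used at sites.

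**Conclusion.** The concern holds. The bound is wrong as written, the error sits in a current operative instruction, and no other current passage sets the minimum. With first-order elimination assumed, the literal text allows between 3.1% and 100% of a torsade-risk drug to remain at restart, against at most 3.1% under the intended rule. This is a range of residual drug, not an estimate of QT risk or of how often the wording would mislead a site. It is a safety-wording error that should be corrected, and it does not touch power, sample size or any planned analysis.

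**What to change.** In Section 5.8, replace the word maximum with minimum in the restart sentence, or say at least five half-lives, and notify sites.

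The direct cost is a one-word protocol correction and a note. Where a site had taken the sentence as a cap, dosing breaks would lengthen to five half-lives. In Cycle 1 that matters only for a concomitant drug with a half-life above 33.6 hours. The patient would then miss more than 25% of the cycle, would not be evaluable for response under Section 3.2, and would be replaced under Section 5.7.1 if the missed dosing was not due to drug-related toxicity. The rule as intended already carries that cost, and it does not arise after Cycle 1.

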6 PHARMACEUTICAL INFORMATION

6.1 Supply of AZD3965

A complete certificate of analysis and a Qualified Person (QP) certification must be supplied with each shipment of AZD3965 and be retained in the Pharmacy File.

For information on AZD3965 and re-ordering of supplies, contact the Clinical Research Associate (CRA)/Clinical Study Manager (CSM) responsible for the trial who will arrange further supplies.

AZD3965 will be supplied by:

Fisher Clinical Services (UK) Limited must send confirmation of shipment to the CRA/CSM once AZD3965 has been despatched to the clinical trial site.

The primary packaging for AZD3965 will be labelled according to Eudralex Volume 4: Annex 13 'Investigational Medicinal Products' of the European Union guide to Good Manufacturing Practice (GMP). An example of the label can be found in the Pharmacy file.

6.2 Pharmaceutical data

6.2.1 Formulation of AZD3965

6.2.2 Storage conditions

All supplies must be stored in a secure, limited access storage area. AZD3965 must be stored at ambient temperature between 15°C and 30°C.

AZD3965 must be stored in its original bottle with the cap on tightly. Study medication must not be refrigerated. Please refer to the current Investigator's Brochure (IB) for detailed information on storage conditions and stability.

Patients must ensure that AZD3965 is kept out of sight and reach of children.

6.2.3 Stability of AZD3965

Please refer to the label on the bottle (primary package) for the expiry date of the unopened AZD3965.

Opened bottles of AZD3965 MUST NOT be refrigerated. Bottles must be stored between 15°C and 30°C and must be kept out of sight and reach of children. Opened bottles of AZD3965 that have passed the expiry date stated on the bottle must be returned to the pharmacy. Patients must close the cap of the bottle tightly immediately after dispensing the number of capsules they are required to take.

Please refer to the current Investigator Brochure for detailed information on storage conditions and stability

6.2.4 Dispensing of AZD3965

Sufficient capsules of AZD3965 must be dispensed on each occasion to cover the prescribed dose over the period to the next scheduled dispensing.

6.2.5 AZD3965 administration

The AZD3965 capsules must be swallowed whole (with water) and not chewed, crushed, dissolved or divided.

AZD3965 should be taken as directed with food. For once daily dosing AZD3965 should be taken at the same time every day and for twice daily dosing AZD3966 should be taken in the morning and 12 hours later.

Should a patient miss a scheduled dose in error, for example, forgetting to take the drug, then AZD3965 may be administered up until 12 hours after the scheduled dosing time (this applies to once a day dosing only). If it is not taken within this time then the patient should wait until the next scheduled dose and continue as per normal drug administration.

If the dosing schedule is twice daily dosing and the patient should miss a dose in error, then AZD3965 may be administered up until two hours after the scheduled time of dose. If it is not taken within this time then the patient should wait until the next scheduled dose and continue as per normal drug administration.

An occasional shift in dosing may be permitted by the CDD to accommodate study visits and study assessments. On these occasions dosing should be brought back to the original dosing schedule as soon as possible.

If the patient vomits after taking the AZD3965 capsule, the patient should not take another capsule and should wait for the next scheduled dose.

On the days of PK sampling (see Section 9.3) patients should take their scheduled dose (morning dose if twice daily dosing) at the hospital so that the exact time of administration can be recorded.

